13.1.3 Recruitment

COMPUTE 2.0 will be conducted at a minimum of 30 primary care clinics within 3 care systems that are geographically dispersed and will include a racially, ethnically and socioeconomically diverse population. Site 1 is HealthPartners, which was the sole site for the COMPUTE 1.0 pilot study, while Site 2 is Geisinger and Site 3 is Essentia. A minimum of 10 primary care clinics to be included per site will be selected in partnership with site PIs and primary care leadership at each site, taking into consideration such factors as overall clinic size, number of waived PCPs, and baseline prevalence of diagnosed OUD. Clinics will be randomized equally within care system

and balanced on pre-randomization outcomes, such as the percentage of study-eligible patients with diagnosed OUD, and on clinic characteristics that may enhance or impede intervention uptake and adherence, such as the number of waived PCPs (see **Section 10.2**).

PCPs who practice at randomized clinics will be asked to complete surveys prior to go-live date and 9-months after go-live date assessing their comfort and confidence treating patients with OUD, and among providers in intervention clinics their perceptions of the OUD-CDS. The DSC will work with the Lead Node and each study site to construct a survey that will be acceptable within each care system. The survey data will be collected by the DSC electronically. Samples for PCP surveys will be identified by the on-site study teams for recruitment and data collection. The DSC will provide each study site with a list of unique survey links, one of which will be included in each invitation to a PCP to respond to the survey. The survey will appear to originate within the health system where possible. All surveys will include a consent form which will allow the respondent to agree to the collection and storage of the respondent's data prior to proceeding with the survey. Clinicians may be offered an incentive for participation.

A sample of patients who have been diagnosed with OUD, have been identified as being at high risk for OUD or opioid overdose, or referred by a PCP will be recruited to participate in surveys and interviews via a mailed or emailed invitation based on standard processes at each site. Samples for evaluation surveys will be defined and identified by the on-site study team for recruitment and data collection. Survey recruitment samples will be balanced by relevant patient characteristics, such as race/ethnicity, gender, or presence/absence of an OUD diagnosis in order to draw generalizations from the survey results. The DSC will work with the Lead Node and each study site to construct a survey that will be acceptable within each care system. The survey data will be collected by the DSC electronically. The DSC will provide each study site with a list of unique survey links, one of which will be included in each invitation to a patient to respond to the survey. The survey will appear to originate within the health system where possible. All surveys will include an informed consent document with the elements of consent for the respondent to agree to prior to proceeding with the survey. Patients will receive a small incentive for survey completion.

Clinic and administrative leaders will be identified as potential candidates for interviews in conjunction with site investigators and healthcare system leadership. Leaders will be emailed an invitation to participate in a phone or in-person interview, and leaders will complete verbal consent to participate at the beginning of the phone interview.

13.1.4 Randomization and Factors for Stratification

The OUD-CDS software is a system-level intervention comprised of 1) a passively operating web service that gathers, analyzes and retains information pertinent to every web service call, and 2) a user interface that presents a summary of algorithm results to front end users. The web service documents every web service call made by all front-end users in all participating locations so that data pertinent to all targeted visits from all eligible and enrolled patients will be identically collected and available in both treatment arms. The user interface will function as the intervention delivery vehicle and therefore be operative only in intervention locations. Intervention or Control designation will vary randomly by clinic. The OUD-CDS web service will therefore operate

passively in all participating clinics but the user interface will only be turned on in clinics that are randomly assigned to the intervention treatment group.

To the extent that patients tend to receive most of their care over time at a single clinic, and that clinicians tend to practice at a single clinic, it is reasonable to assert that the risk of intervention contamination across clinics is low. However, because it is common for patients to see more than one clinician in a clinic location over time, and for clinicians within a clinic location to discuss aspects of care delivery with each other, the risk of intervention contamination within clinics is rather high. Randomizing by clinic rather than by PCP or patient will minimize risk of intervention contamination.

Generally speaking, randomization should balance treatment groups on factors that enhance or impede intervention uptake and adherence, that are related to and including study outcomes, and on any other unmeasured factors that may affect statistical power. However, the likelihood that factors related to these considerations are balanced may be diminished in cluster-randomized trials due to relatively few randomized units.[33, 34] Covariate constrained randomization will be implemented to balance treatment groups across the study and within health care systems (strata) on factors related to study outcomes, implementation of the intervention, and potential treatment modifiers.

Potential balancing factors include:

- n of waived providers
- n of adult patients at clinic
- % of adult patients with government sponsored insurance
- % of adult patients who are non-Hispanic White
- % of all patients at high risk for OUD
- % of patients at high risk for OUD provided a with naloxone rescue kit
- % of all patients with diagnosed OUD
- % of all patients with diagnosed OUD with a current MOUD

Each patient will be assigned to the clinic in which his or her first visit that is eligible for the OUD-CDS intervention (i.e., index visit) takes place, and as such will be assigned to the treatment group to which their clinic was randomly assigned. Post-index visits may take place in the same or different clinics or treatment groups relative to the index visit and may or may not be eligible for the OUD-CDS to offer treatment recommendations. In keeping with an intent-to-treat principle, all index and post-index visits and outcome measures for each patient will be attributed to the treatment group assignment of the clinic where the index visit took place.

Further details regarding the randomization procedures including the final balancing factors included in the randomization are provided in a separate study randomization plan.

13.1.5 Prediction Models

Aims 1 through 3 pertain to the effectiveness of the OUD-CDS intervention relative to UC, predicting that it will increase diagnosis, naloxone prescribing, and access to MOUD, and decrease ED visits and inpatient stays. These hypotheses will be tested using generalized linear mixed models to account for clustering of outcomes within eligible patients and randomized clinics, or using generalized estimating equations to compare event rates. Outcomes will be normalized via distribution-appropriate link functions (e.g., logistic-Normal, Poisson-Normal).

Clinic-randomized treatment group, care system and other predictors will be treated as fixed effects.

13.2 Rationale for Sample Size and Statistical Power

13.2.1 Projected Number of Sites

At least 30 primary care clinics at three participating healthcare systems (i.e., at least 10 primary care clinics per healthcare system) are expected to participate in this study.

13.2.2 Projected Number of Participants per Site

There must be at least 50 patients with or at high risk for OUD at an index visit at a randomized clinic for it to be included in the analyses. Based on the number of patients with study-eligible visits in the COMPUTE 1.0 pilot study, we expect this will be a low threshold for clinics to attain. The COMPUTE 1.0 intervention was implemented for six months among 55 randomized providers who practiced in 30 clinics. During that time, these providers saw between 14 and 137 patients (provider median = 77; 37-412 patients per clinic, clinic median = 163) who were eligible for the pilot OUD-CDS intervention. To the extent the COMPUTE 2.0 intervention is expected to collect outcome data on patients for 19 to 31 months in the randomized clinics, and study-eligible patients will be seen by all clinic providers, it is plausible to expect that 1,000 study-eligible patients could have index visits at many clinics.

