- Varies by system
- OUD-CDS implementation date through a predetermined time at which the Wizard interfaces will be turned off in the intervention clinics

Accrual Period

- Varies by system
- OUD-CDS implementation date through a predetermined time at which no more people will be included in the analytic sample

Index Date

- Varies by patient
- First visit at which the OUD-CDS identifies that the patient is study eligible

Observation Period

- Varies by patient
- Index visit date through a predetermined time at which outcome data will no longer be accumulated

H1.2: Patients previously diagnosed with OUD or identified as high risk by the OUD-CDS at an index visit will be more likely to have naloxone rescue kits ordered in the intervention clinics than in the UC clinics within 30 days post-index.

Aim 2. To assess the impact of OUD-CDS on important patient outcomes of initiation and maintenance of Medications for Opioid Use Disorder (MOUD) in patients identified as having OUD or being at high risk for OUD.

H2.1: Patients identified as having OUD or as being at high-risk for OUD by the OUD-CDS at an index visit will be more likely to have MOUD orders or referral for OUD treatment within 30 days post-index in intervention clinics than in UC clinics.

H2.2: Patients identified as having OUD or as being at high-risk for OUD by the OUD-CDS at an index visit will have significantly more days covered by a MOUD prescription at 90 days post-index in intervention clinics than in UC clinics.

Aim 3. To assess the long-term impact of OUD CDS on important patient outcomes in patients with OUD or identified as high risk for OUD.

H3.1: Patients with OUD or identified as high-risk for OUD by the OUD-CDS who are cared for in intervention clinics will have significantly fewer post-index emergency department (ED) visits during the observation period (i.e., the period between each patient's index date and last observation) compared to patients cared for in UC clinics.

H3.2: Patients with OUD or identified as high-risk for OUD by the OUD-CDS who are cared for in intervention clinics will have significantly fewer post-index hospitalizations during the observation period compared to patients cared for in UC clinics.

Aim 4. To describe and quantify costs of OUD-CDS implementation and maintenance and the short-term cost impacts of the OUD-CDS.

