2.3 Sample Size and Study Population

The study will be conducted at a minimum of 30 primary care clinics within 3 healthcare systems in the United States that are geographically dispersed and will include a racially, ethnically and socioeconomically diverse population. Clinics will be randomized equally within each care system and balanced on pre-randomization outcomes, such as the percentage of patients at high-risk or with diagnosed OUD, and on clinic characteristics that may enhance or impede intervention uptake and adherence, such as the number of buprenorphine-waivered PCPs (see **Section 10.2**). PCPs who practice at randomized clinics will be asked to complete pre-and post-implementation surveys assessing their comfort and confidence treating patients with OUD. Primary and secondary outcomes data will be collected from the EHR or CDS tool for each patient with an

eligible index visit. Following intent-to-treat principles, all PCPs and eligible patients will be attributed to the arm to which their clinic is randomly assigned. Surveys will also ask providers in intervention clinics about their perceptions of the OUD-CDS. Additionally, we will conduct surveys with patients and interviews with PCPs, clinic staff, clinic leaders and patients to understand their perceptions of the acceptability of OUD treatment in primary care and their impressions of the OUD-CDS to help improve the implementation and uptake of the OUD-CDS.

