7.2 Study Timeline

After receiving Center for the Clinical Trials Network (CCTN) approval of the final protocol, approximately 9-12 months of trial preparation activities will elapse prior to commencing enrollment (“go-live”) at Site 1. The intervention at Site 2 is anticipated to begin 6-9 months after go-live date at Site 1, and the intervention at Site 3 will begin 12-15 months after the go-live date at Site 1. Selection of Geisinger as Site 2 and Essentia as Site 3 occurred subsequent to the initial CCTN approval of the final protocol and initial IRB submission. Trial preparation will include obtaining Institutional Review Board (IRB) approval, customizing the OUD-CDS for each healthcare system, harmonizing data elements for EHR installation at each site, installing of EHR custom code at each site, recruiting and randomizing primary care clinics at each site, conducting PCP training at each site, integration of CDS into workflow at each site, and completing baseline PCP surveys at each site.

As noted previously, the COVID-19 pandemic delayed implementation by approximately 8 months. Accrual periods will range from 7 to 18 months based on site. During the accrual period, the study team will monitor accrual rates to determine when a sufficient number of patients have been enrolled to support the analysis plan. If enrollment is lower than expected, we may choose to extend the accrual period up to 3 additional months (through January 2023). Observation will begin with index dates at each site and are anticipated to continue through October 2023.

Anticipated Accrual + Observation Periods per Site:

- HealthPartners – April 2021 to Oct 2023 (31 months)
- Geisinger – Dec 2021 to Oct 2023 (22 months)
- Essentia – April 2022 to Oct 2023 (18 months)

Anticipated Accrual* Periods per Site:

- HealthPartners – April 2021 to Oct 2022 (18 months)
- Geisinger – Dec 2021 to Oct 2022 (10 months)
- Essentia – April 2022 to Oct 2022 (7 months)

* We may extend the accrual period an additional 3 months based on enrollment trends.

COMPUTE 2.0 Study Timeline

Study Timeline	Year 1		Year 2				Year 3				Year 4				Year 5		
	2019		2020		2021		2022		2023		2024						
	Quarter	3	4	1	2	3	4	1	2	3	4	1	2	3	4	1	2
Phase 1: Development Phase																	
Finalize protocol, obtain IRB approval (Site 1)																	
Obtain IRB approval at Sites 2 & 3																	
Customize OUD-CDS for each partner site																	

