8.0 STUDY POPULATION

8.1 Primary Care Clinics

This randomized clinical trial is a clinic-randomized study. A minimum of ten primary care clinics to be included in the study at each of three sites will be selected in partnership with primary care leadership at each site. To be eligible for randomization in this study, a primary care clinic must: (a) be included in one of the three care delivery systems included in this study, (b) have a minimum of 3 full-time PCPs who do not regularly work at any other primary care clinic, and (c) have an estimated minimum of 50 adult patients who meet study criteria for OUD or high risk for OUD. Exclusion criteria for potentially eligible primary care clinics include (a) plans to close or transfer ownership of the clinic within 24 months after the anticipated OUD-CDS go-live date, or (b) clinic not using their current EHR system for at least 12 months before the anticipated OUD-CDS go-live date at the clinic. Primary care clinics that have fewer than 50 patients at risk for OUD may not be eligible for randomization. However, consideration will be given to small clinics that may be part of a larger spoke and hub primary care clinic system, depending on the organizational structure of included care systems. For example, clinics X and Y in healthcare system 2 may be too small to consider randomizing them on their own, but because they are affiliated with clinic Z and most PCPs at clinic Z practice a day or two a week at clinics X and Y, clinics X, Y and Z would be randomized as one potential unit (thereby avoiding potential contamination).

Primary care clinics that pass all these eligibility and exclusion criteria will be randomized (within study site) using a validated computer-generated randomization scheme that takes into consideration such factors as overall clinic size, number of PCPs, number of buprenorphine PCPs, and baseline prevalence of diagnosed OUD. All PCPs and their study-eligible patients will be assigned to the treatment group of their randomized primary care clinic.

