selected based on their ability to provide diversity in primary care practices, patient race and ethnicity, geographic distribution, and rural/urban representation.

Primary Care Clinics

In this clinic-randomized trial, decisions about which primary care clinics may be ineligible for inclusion will be made in partnership with primary care leadership. Primary care clinics that have fewer than 50 patients meeting eligibility criteria may not be eligible for randomization. However, consideration will be given to small clinics that may be part of a larger spoke and hub primary care clinic system, depending on the organizational structure of included care systems. For example, clinics X and Y in healthcare system 2 may be too small to consider randomizing them on their own, but because they are affiliated with clinic Z and most PCPs at clinic Z practice a day or two a week at clinics X and Y, clinics X, Y and Z would be randomized as one potential unit (thereby avoiding potential contamination).

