10.2 Randomization

The OUD-CDS software is a system level intervention comprised of 1) a passively operating web service that gathers, analyzes and retains information pertinent to every web service call, and 2) a user interface that presents a summary of algorithm results to front end users. The web service documents every web service call made by all front-end users in all participating locations so that data pertinent to all targeted visits from all eligible and enrolled patients will be identically collected and available in both treatment arms. The user interface will function as the intervention delivery vehicle and therefore be operative only in intervention locations. Intervention or Control designation will vary randomly by clinic. The OUD-CDS web service will therefore operate passively in all participating clinics but the user interface will only be turned on in clinics that are randomly assigned to the intervention treatment group.

To the extent that patients tend to receive most of their care over time at a single clinic, and that clinicians tend to practice at a single clinic, it is reasonable to assert that the risk of intervention contamination across clinics is low. However, because it is common for patients to see more than one clinician in a clinic location over time, and for clinicians within a clinic location to discuss aspects of care delivery with each other, the risk of intervention contamination within clinics is rather high. Randomizing by clinic rather than by PCP or patient will minimize risk of intervention contamination.

Generally speaking, randomization should balance treatment groups on factors that enhance or impede intervention uptake and adherence, that are related to and including study outcomes, and on any other unmeasured factors that may affect statistical power. However, the likelihood that factors related to these considerations are balanced may be diminished in cluster-randomized trials due to relatively few randomized units.[33, 34] Covariate constrained randomization of the clinics will be implemented to balance treatment groups across the study and within health care systems (strata) on factors related to study outcomes, implementation of the intervention, and potential treatment modifiers. Potential balancing factors include:

- % of all patients with diagnosed OUD with a current MOUD
- % of all patients with diagnosed OUD
- % of all patients at high risk for OUD

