- % of patients at high risk for OUD provided a with naloxone rescue kit
- n of adult patients at clinic
- % of adult patients with government sponsored insurance
- % of adult patients who are non-Hispanic White
- n of waived providers

Each patient will be considered to belong to the clinic in which his or her first visit that is eligible for the OUD-CDS intervention (i.e., index visit) takes place, and as such will be in the treatment group to which their clinic was randomly assigned. Post-index visits may take place in the same or different clinics or treatment groups relative to the index visit and may or may not be eligible for the OUD-CDS to offer treatment recommendations. In keeping with an intent-to-treat principle, all index and post-index visits and outcome measures for each patient will be attributed to the treatment group assignment of the clinic where the index visit took place.

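### Section 13.2.2 makes a randomized clinic's place in the analyses depend on reaching 50 index patients, a count that exists only after randomization

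*Combined protocol and SAP*

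**What the plan says.** The number 50 appears in two roles.

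- **Eligibility for randomization.** Section 8.1 lists, among the conditions a clinic must meet to be randomized, that it "have an estimated minimum of 50 adult patients who meet study criteria for OUD or high risk for OUD". Section 9.3 says "Primary care clinics that have fewer than 50 patients meeting eligibility criteria may not be eligible for randomization". Both sections allow small affiliated clinics to be combined and randomized as one unit.
- **Inclusion in the analyses.** As a condition for a clinic to enter the analyses, section 13.2.2 asks for "at least 50 patients with or at high risk for OUD at an index visit at a randomized clinic for it to be included". It expects clinics to reach this level without difficulty.

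Three other parts of the protocol bear on the point.

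- **Timing.** Section 7.2 places "recruiting and randomizing primary care clinics at each site, conducting PCP training at each site" within trial preparation, before go-live. Section 2.1 defines the index date as the first visit at which the OUD-CDS flags a patient as eligible, and the accrual period as "OUD-CDS implementation date through a predetermined time at which no more people will be included in the analytic sample".
- **Intent to treat.** Section 2.3 states "Following intent-to-treat principles, all PCPs and eligible patients will be attributed to the arm to which their clinic is randomly assigned". Sections 10.2 and 13.1.4 attribute each patient's visits and outcomes to the arm of the index clinic.
- **Balance.** Sections 10.2 and 13.1.4 use covariate-constrained randomization because few units are randomized and chance imbalance is a worry.

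**The concern.** Sections 8.1 and 9.3 rely on an estimate made before allocation. Section 13.2.2 applies to clinics already randomized and counts patients who do not yet exist when the clinic is allocated. An analyst who follows 13.2.2 would delete any randomized clinic that ends accrual with fewer than 50 index patients. An analyst who follows 8.1 and 9.3 would keep it. No other section settles which reading applies or says what happens to an excluded clinic's patients.

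The clinic is the unit of randomization, so deleting one loses a whole cluster and can disturb the balance that the constrained randomization was meant to secure. It also sits poorly with the statement in section 2.3 that covers all eligible patients. If only the minimum of 30 clinics is randomized, any deletion leaves fewer than 30 in the analysis.

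The planned models do not need a floor. Section 13.3 specifies clinic random intercepts for Aims 1 and 2, and a log patient-year offset for the clinic counts of Aim 3. Both accommodate small clinics.

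**Working it through.** **1. Order of events.** Clinics are randomized in preparation (7.2). The OUD-CDS then goes live, index visits occur and the count builds (2.1, 10.1). The count named in 13.2.2 cannot be known at randomization, so the rule as worded acts after it.

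**2. Could a clinic fall short?** In the six-month pilot, 55 providers in 30 clinics saw 37 to 412 eligible patients per clinic, median 163 (13.2.2). Accrual here runs from 7 to 18 months, with an optional 3-month extension (7.2). Scaling the smallest pilot clinic:

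- By time alone: 37/6 × 7 = 43 at 7 months, and 37/6 × 10 = 62 at 10 months.
- By time and providers: the pilot average was 55/30 = 1.83 providers per clinic. If the smallest clinic had that many (an assumption), scaling to the 3 full-time PCPs that 8.1 requires gives 43.2 × 3/1.83 = 71 at 7 months.

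Few clinics, if any, would fall short.

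**3. The plan's own figure.** Section 13.2.2.1 gives 11.35% as detectable against 5%, with 30 clinics of 50, ICC 0.03, power 0.80 and two-sided 5%. The method used here is:

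- Effective n per arm = ½ × Σ m/(1 + (m − 1) × ICC) over the analysed clinics, assuming equal arms.
- SE = √{[p₁(1 − p₁) + p₂(1 − p₂)]/n}.
- Power from a noncentral t-test with df = analysed clinics − 2.

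For 30 clinics of 50, effective n per arm = 15 × 50/2.47 = 303.6, SE = 0.0221 and (0.1135 − 0.05)/0.0221 = 2.87. With 28 df, power is 0.793, and the rate detectable at 0.80 is 11.42%. This agrees closely with the plan.

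**4. Information in a small clinic (ICC 0.03).** The effective patient count is m/(1 + (m − 1) × 0.03): 16.0 for m = 30, 20.2 for m = 50 and 30.4 for m = 333. A clinic below 50 still contributes usefully.

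**5. Power with short clinics kept or dropped.** Section 14.3.1 expects more than 10,000 patients, so about 10,000/30 = 333 per clinic. The number and size of short clinics are assumptions.

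| Short clinics | Other clinics | ICC; rates | Kept | Dropped | Loss (points) |
|---|---|---|---|---|---|
| one of 30 | 333 | 0.03; 5% vs 11.35% | 0.921 | 0.916 | 0.5 |
| two of 30 | 333 | 0.03; 5% vs 11.35% | 0.917 | 0.906 | 1.1 |
| four of 30 | 333 | 0.03; 5% vs 11.35% | 0.908 | 0.882 | 2.6 |
| four of 20 | 333 | 0.03; 5% vs 11.35% | 0.904 | 0.882 | 2.2 |
| four of 40 | 333 | 0.03; 5% vs 11.35% | 0.911 | 0.882 | 2.9 |
| four of 30 | 333 | 0.01; 5% vs 9.80% | 0.982 | 0.977 | 0.6 |
| four of 30 | 333 | 0.05; 5% vs 12.89% | 0.880 | 0.844 | 3.6 |
| one of 30 | 50 | 0.03; 5% vs 11.35% | 0.790 | 0.778 | 1.2 |
| four of 30 | 50 | 0.03; 5% vs 11.35% | 0.781 | 0.729 | 5.3 |
| four of 20 | 50 | 0.03; 5% vs 11.35% | 0.772 | 0.729 | 4.4 |
| four of 40 | 50 | 0.03; 5% vs 11.35% | 0.788 | 0.729 | 5.9 |

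Losses are taken before rounding the powers. The calculation treats each clinic's index count as its H1.1 sample. The true H1.1 sample is smaller, because it covers only high-risk patients without an earlier diagnosis.

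**The case against.** The strongest reply is that this is a planning sentence. It stands under a heading on projected numbers and leads into pilot counts and power. Fifty is the smaller of the two cluster sizes assumed there. The sections that govern the analysis (13.3, 13.4, 13.7) contain no such exclusion, and section 13.3 leaves methodological decisions to a separate Statistical Analysis Plan. This may well explain how the sentence arose. Its wording nevertheless speaks of a randomized clinic and of inclusion in the analyses, and no section overrides it.

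It can also be said that no clinic will be short. The optional extension would take the shortest accrual from 7 to 10 months, where even the time-only scaling gives 62. That stands, and is why the point is minor. The extension is discretionary, however, and the pilot minimum of 37 shows that a count below 50 is possible.

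On bias, section 6.2 has the algorithms identify patients in both arms without depending on what PCPs do, so the count need not differ by arm. That too stands. The intent-to-treat statements concern attribution to arm and do not expressly forbid dropping a clinic. Disturbed covariate balance is a possibility that has not been demonstrated.

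On the arithmetic, the scenarios with other clinics at 333 total slightly under 10,000 (for example 26 × 333 + 4 × 30 = 8,778), and equal arms cannot hold exactly when one clinic is dropped. Neither changes the order of magnitude.

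**Conclusion.** The concern holds as a defect of wording, with high confidence. Section 13.2.2 states a post-randomization exclusion of clusters that 8.1 and 9.3 do not contain and that the planned models do not require.

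Its size is minor. Few clinics, if any, are likely to be affected, and nothing here shows that any will be dropped. At about the projected enrolment, with ICC 0.03, losing one to four 30-patient clinics costs 0.5 to 2.6 points of power. Across the ICCs of Table 3, losing four costs 0.6 to 3.6 points. A loss of about 5 points needs four short clinics and every other clinic at exactly 50, against a pilot median of 163 in six months. All these figures rest on assumed numbers and sizes of short clinics. Arm-related bias is probably small.

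**What to change.** Reword 13.2.2 so that 50 is an estimate used before randomization to judge eligibility, as in 8.1 and 9.3. Add that every randomized clinic, or group of affiliated clinics randomized as one unit, with at least one index patient is analysed in its assigned arm. If a restriction to clinics with 50 or more index patients is wanted, keep it as a sensitivity analysis. Put the same wording in the Statistical Analysis Plan, before outcome data are seen.

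The cost is one sentence in the protocol, repeated in the Statistical Analysis Plan, plus the sponsor agreement and IRB approval that sections 14.1 and 14.2 require for any amendment. Clinic operations and data collection do not change.
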